
**Power Calculations:** We assess the power to detect effects that are clinically meaningful and realistic. For this calculation, we assess the power to detect at least 80% power of a 2-sided significance test with  $\alpha = 0.05$ . We are interested in comparing the rate of HPV completion in the sixth quarter after intervention with HPV completion rate at baseline. Given the following conditions: 1) Pre-specified total sample size of 40 practices; 2) Design (stepped-wedge with five cohorts of eight practices starting six months apart); 3) Two-sided significance level of 0.05; 4) Starting practice-level HPV completion of 24% as described above; 5) Intra-cluster correlation (ICC) of patients within practices of 0.08 (82, 83), we will have at least 80% power to detect a minimum of 19.4% difference in the absolute change (increasing from 24.0% to 43.4%). If we are successful at retaining all 45 practices that will be recruited, we will have at least 80% power to detect a 18.1% difference in absolute change. These estimates assume a conservative ICC of 0.08. As most studies show an  $ICC < 0.001$  (84), the proposed study will have sufficient power to detect differences of health policy importance. Estimates of parameters for these power

calculations were obtained from model (1) and the most recent, up-to-date OIP dataset. These power calculations estimate the minimum numbers needed to detect minimum changes.

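### The stated minimum detectable differences (19.4 points with 40 practices, 18.1 with 45) are well above what model (1) gives at any practice size compatible with Table 1, and the practice size used is not stated

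*Combined protocol and SAP*

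**What the plan says.** The Power Calculations paragraph of section 13.0 opens with an aim: "We assess the power to detect effects that are clinically meaningful and realistic". The target is a contrast over time: "We are interested in comparing the rate of HPV completion in the sixth quarter after intervention with HPV completion rate at baseline".

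Five conditions are listed: 40 practices; a stepped wedge with "five cohorts of eight practices starting six months apart"; a two-sided 0.05 level; "Starting practice-level HPV completion of 24% as described above"; and an ICC of 0.08. The result with 40 practices is at least 80% power "to detect a minimum of 19.4% difference in the absolute change (increasing from 24.0% to 43.4"%). If all 45 recruited practices are retained, "we will have at least 80% power to detect a 18.1% difference in absolute change". The parameter estimates for the power "calculations were obtained from model (1) and the most recent, up-to-date OIP dataset", and the paragraph closes: "These power calculations estimate the minimum numbers needed to detect minimum changes".

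Earlier in section 13.0, model (1) is a Poisson mixed model with a random practice intercept, a linear time trend, an immediate intervention effect (beta2), an effect that grows with exposure (beta3), and log(E_it) as offset, over 14 quarterly points. E_it is defined there but given no value. Table 1 in section 4.0 plans 21,574 adolescents. Section 5.0 rests the need for 40 practices on the sample size estimates.

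**The concern.** A detectable difference in a clustered design depends on how many patients each practice contributes per period. That number is missing, so the five conditions cannot produce 19.4 or 18.1, and nobody outside the team can check them.

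The size of the figures is also surprising. Going from 24.0% to 43.4% is a relative rise of 19.4/24.0 = 81%. A stepped wedge with 40 practices, 14 quarters and a random practice intercept draws most of its information from within-practice change and would normally detect much less. A reader who takes the figure as a true minimum will conclude that gains of, say, 8 to 15 points are beyond this trial. That bears on whether the target effect is realistic, and on how a modest result would be read.

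**Working it through.** **Inputs from the documents.** 40 practices (5 cohorts of 8) or 45 (5 of 9); cohorts two quarters apart; 14 quarters; baseline 24%; ICC 0.08; two-sided 0.05; 80% power; 21,574 adolescents.

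**Assumptions.** The first cohort crosses over at t = 1, 2, 3 or 4 (the timeline figure is not visible). Practices are of equal size, with m patients per practice-quarter. 24% is the rate applied to those m patients.

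**Method.** Generalised least squares on the practice-by-quarter log rates.
- Practice variance: 0.08 × 0.76/0.24 = 0.253.
- Residual variance: 1/(m × 0.24).
- Sixth-quarter contrast: beta2 + 5·beta3, or beta2 + 6·beta3 if that quarter is read as t − s = 6.
- Detectable difference in points: 24 × [exp(2.802 × SE) − 1], where 2.802 = 1.960 + 0.842.
- Time is linear, as in model (1), or categorical as a variant.

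**Step 1: what the stated figures require.** 19.4 points needs SE = ln(43.4/24.0)/2.802 = 0.5924/2.802 = 0.211. 18.1 points needs SE = ln(42.1/24.0)/2.802 = 0.5620/2.802 = 0.201. Solving for m:

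| Specification | 19.4 with 40 practices | 18.1 with 45 practices |
|---|---|---|
| beta2 + 5·beta3 | 3.2–4.9 | 3.2–4.8 |
| beta2 + 6·beta3 | 4.1–6.6 | 4.1–6.5 |
| Separate effect per exposure quarter (not model (1)) | 6.9–9.6 | 6.8–9.5 |

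Simulation of the Poisson mixed model with 40 practices agrees: power at 43.4% was 0.63–0.75 with 3 patients and 0.81–0.90 with 4. Treating practices as fixed effects needs about 6–8.

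**Step 2: what Table 1 implies.** 21,574/40 = 539 adolescents per practice. Counting each in only one of 14 quarters gives 539.4/14 = 38.5; with 45 practices, 21,574/45/14 = 34.2. By contrast, 5 patients × 40 practices × 14 quarters = 2,800 patient-quarters, 13% of 21,574 even if nobody is counted twice.

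A deliberately low reading takes 60 practices (section 8.0 says 40–60), ages 13–17 only (Table 2's range for completion; 5/7 assumes even ages), only the 76% not yet complete, and each counted once: 21,574/60 × 5/7 × 0.76/14 = 13.9.

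**Step 3: detectable difference at those sizes, 40 practices.** For example, at m = 38.5 with linear time and first crossover at t = 1, SE = 0.0904 and 24 × [exp(0.2533) − 1] = 6.9 points. With first crossover at t = 4, SE = 0.0687 and the result is 5.1.

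| Patients per practice-quarter | beta2 + 5·beta3 | Same, cluster autocorrelation 0.5 (outside model (1)) |
|---|---|---|
| 13.9 | 8.8–12.1 | 10.1–12.5 |
| 38.5 | 5.1–7.3 | 7.5–9.8 |
| 539 | 1.3–1.9 | not run |

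At 38.5 with t − s = 6 the range is 5.7–8.3. With 45 practices at 34.2 it is 5.1–7.3. Simulation with fixed practice effects runs a little higher: at 38.5, 80% power needed up to 24.0% to 31.7% (7.7 points); at 13.9, up to 24.0% to 37.7% (13.7 points). At 13.9 with first crossover at t = 1, power at 43.4% was 0.97 (linear time) and 0.96 (categorical).

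**Step 4: a calculation that comes close.** A parallel comparison of one cohort with another, g practices a side and m patients each, gives d = 2.802 × sqrt{[p1q1 + p2q2] × [1 + (m − 1) × 0.08]/(m × g)}. At an assumed m = 100:
- g = 8: 2.802 × sqrt{0.4280 × 8.92/800} = 19.4 points.
- g = 9: 2.802 × sqrt{0.4263 × 8.92/900} = 18.2 points.

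**The case against.** The strongest reply is that no sum is wrong. 24.0 + 19.4 is 43.4, and an unstated input is a reporting gap. The text says only that parameter estimates came from model (1); it does not say that power was computed as a test of this contrast. Table 1 is census-based, section 8.0 also admits residents of clinic catchment areas, and E_it is a different quantity. Completion during a quarter might mean new completions, in which case 24% does not apply to every counted adolescent each quarter. All of this stands, and it is why no single replacement figure follows. It does not rescue the minimum: even 13.9 patients per practice-quarter leaves the detectable difference well short of 19.4, and the new-completions reading does not by itself bring model (1) to 19.4.

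A second reply is that caution is sensible, because a random intercept alone is optimistic. Stacking illustrative assumptions (autocorrelation 0.8, practice-size coefficient of variation 1, random-effect SD 0.3, slope SD 0.1 per quarter) gives 14.6–15.1 points at 38.5 and 18.4–19.3 at 13.9. None of these is in model (1) or stated in the plan. The argument does show that replacing 19.4 with a bare random-intercept value would be too optimistic.

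Third, the plan calls its ICC of 0.08 conservative. In model (1), however, the practice intercept largely cancels from a within-practice contrast. In one configuration of the check, raising its variance from 0.253 to 1.0 moved the required size only from 4.7 to 6.4 patients.

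A reader might also object that the 24% is given without a source. Its source may lie in text removed from the version available, so this is not counted against the plan.

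**Conclusion.** The point holds as a mismatch between a stated minimum and the model named beside it. Under model (1) the two figures need about 3–7 patients per practice-quarter, up to about 10 with variant specifications. At about 38 the detectable difference is about 5–8 points, or about 7.5–10 with cluster autocorrelation 0.5; at 14 it is about 9–14. These ranges rest on the assumed crossover quarter, equal practice sizes, and the assumed link between Table 1 and E_it. The mismatch is robust across those choices; the exact replacement is not known.

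Two stronger readings are tempting, and the documents support neither. One is that the trial is underpowered: the discrepancy runs the other way, and at least 80% power at 19.4 points holds at every size derived from Table 1 under model (1). The other is that the sponsor used a cohort-against-cohort calculation: the resemblance is close, but it depends on an assumed 100 patients per practice and nothing in the documents confirms it.

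**What to change.** Recompute the sixth-quarter contrast from the stepped-wedge model for 40 and 45 practices, taking E_it from the OIP data. Beside the result, state:
- E_it, its age range and its relation to Table 1;
- whether completion means coverage or new completions in the quarter;
- the variance components and the first crossover quarter;
- the formula or software.

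Show sensitivity values for practice-by-period variation and over-dispersion next to the model (1) value, and replace 19.4 and 18.1 with that range. If the two figures came from a simpler calculation, say so and stop presenting them as the minimum for this design.

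The cost is one recalculation and a revised paragraph in section 13.0. Enrolment, the 40 and 45 practices, and the design do not change.

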## 13.0 BIO-STATISTICAL CONSIDERATIONS

Our proposed stepped-wedge cluster randomized trial (78) will evaluate the impact of the proposed intervention on HPV outcomes in 40 primary care practices (Aim II). We will specifically test two hypotheses: 2a) More patients will have initiated and completed the HPV vaccine series in intervention practices compared to control practices, and 2b) Practices receiving the intervention will have lower rates of missed opportunities to vaccinate compared to control practices. The primary outcome variables will include receipt rate of the initial (age 11-12 years) and full series of HPV vaccines and a reduction in the rates of missed opportunities to vaccinate among males and females aged 11-17 years. We will conduct block randomization of practices in five waves every six months. Outcomes will be measured every three months in all clusters at every period, so that each cluster provides data points in both the control and intervention conditions. Practices in each wave will be stratified based on designation of pediatric or family medicine clinic to balance pediatric/family medicine clinics at each wave. Outcome data collection will be collected from ALERT IIS beginning in quarter four of the study and up to 17, for 14 longitudinal data collection points per practice. [name], who has no contact with the study practices, will perform the randomization for all practices prior to the start of the first intervention wave. Randomized assignment will not be revealed to practices until their cluster begins the study.

The primary goal of Aim II is to establish whether the intervention is effective and the degree to which it is accomplishing its goals. Our outcome evaluation includes a rigorous research design so we may attribute positive findings to the intervention and not to existing threats to internal validity. To compare the effect of the intervention with usual care on HPV outcome measures in the context of a stepped-wedge design, we will utilize Generalized Linear Mixed Models (GLMMs) (79). In particular, to assess the intervention effect, we will use a Poisson model with random effects for practice. The general model is as follows:

$$(1) \log(Y_{it}|b_i) = \beta_0 + \beta_1 t + \beta_2 I_{it} + \beta_3 I_{it}(t - s_i) + \beta_4 Z_i + b_i + \log(E_{it})$$

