Analysis Considerations: If we find significant practice differences between cohorts, we will utilize propensity score weighting methods to reduce the observed bias, help minimize external threats to the validity of results, and adjust for imbalances (85, 86). Additionally, model (1) can accommodate missing data resulting from practice attrition. We will explore model missingness by including relevant variables in the analysis as covariates (87, 88). If non-trivial levels of missing data are observed, we will use methods such as multiple imputation to include these practices in analyses (87). We will conduct a sensitivity analysis comparing parameter values for models using completers only, all practices without multiple imputation, and all practices with multiple imputation, to understand any biases introduced by differential attrition or missing not at random (88). Our project has control, intervention, and follow-up periods in all seasons, which will allow us to detect and account for the potential effect of seasonality on the receipt of indicated adolescent vaccines.

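### The plan does not say whether registry outcomes are still extracted after a practice withdraws, and agreement among its three planned sensitivity fits says nothing about missing-not-at-random bias

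*Combined protocol and SAP*

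**What the plan says.** All references are to the combined protocol and SAP.

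- **Measurement (13.0, opening paragraph).** Outcomes come from the ALERT IIS registry. "Outcomes will be measured every three months in all clusters at every period", giving "14 longitudinal data collection points per practice".
- **Exposure (13.0, definitions under model (1)).** The intervention indicator is set by assignment, not by continued participation.
- **Attrition (13.0, Analysis Considerations).** The plan states that "model (1) can accommodate missing data resulting from practice attrition". If missingness is more than trivial, "we will use methods such as multiple imputation to include these practices in analyses".
- **Sensitivity analysis (same paragraph).** It compares "models using completers only, all practices without multiple imputation, and all practices with multiple imputation", with the aim "to understand any biases introduced by differential attrition or missing not at random". Covariates related to missingness are also to be explored.
- **Numbers (5.0, and 13.0 Power Calculations).** Forty practices are needed and 45 are enrolled to allow for 11% attrition. The smaller detectable difference of 18.1 points applies "If we are successful at retaining all 45 practices that will be recruited".

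Attrition is not defined. Neither 9.0 (ALERT IIS abstraction) nor 13.0 says what happens to extraction when a practice stops taking part.

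**The concern.** Outcomes come from a state registry, not from forms that the practice fills in for the study. A practice can therefore stop the intervention while its patients' vaccinations are still recorded. Two analysts could follow section 13.0 in good faith and build different primary datasets. One would keep all 14 quarters for every randomised practice. The other would cut a leaver's series at exit and rely on model (1) or imputation.

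The choice decides which effect is estimated. The first dataset gives the effect of assignment. The second gives the effect as if leavers had carried on. The planned sensitivity comparison would not show the difference, because none of its three fits contains anything about leavers after exit. Close agreement could then be taken as reassurance that it cannot give.

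**Working it through.** **1. The plan's attrition figure.** Inputs from 5.0: 40 needed, 45 enrolled, 11%. 40/0.89 = 44.9, rounded up to 45, and 5/45 = 11.1%. The figure reproduces.

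**2. The passages side by side.** The measurement schedule and the as-assigned coding together suggest that leavers keep contributing data. Analysis Considerations treats attrition as a cause of missing values in model (1), whose numerator and denominator are the registry outcome counts. Both statements can stand if attrition means only that registry data are absent, but the plan does not say so.

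**3. What each planned fit assumes.**
- *Completers only* uses only practices that stayed. It needs leavers to resemble stayers in their effect.
- *All practices without imputation* is a likelihood fit of model (1) to the observed quarters. It assumes missing at random, given what is in the model.
- *All practices with standard multiple imputation* draws the missing quarters from a model fitted to the observed ones. It makes the same assumption, so it should reproduce the previous fit apart from simulation noise or extra imputation covariates.

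Leavers' post-exit outcomes enter none of the three. If those outcomes change and everything before exit stays the same, all three results are unchanged.

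**4. Numerical illustration, on assumed values.** The set-up was 45 practices, 14 quarters and assumed starts at t = 2, 4, 6, 8 and 10. A log-rate version of model (1) was used, with a true rate ratio of 1.284 in the sixth intervention quarter. Five practices chosen at random left one quarter after their start.

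| Leavers after exit | Completers | All, no imputation | All, imputed | Full registry |
|---|---|---|---|---|
| keep the effect | 1.286 | 1.285 | 1.285 | 1.286 |
| lose it all | 1.283 | 1.284 | 1.284 | 1.249 |

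The three planned fits agree to within about 0.001 in both rows. Only the full-registry column shows the difference. The effect size, starts and exit time are not from the plan, so the table shows the pattern and does not calibrate this trial.

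**5. Size at the planned attrition.** Inputs from Power Calculations: 19.4 points detectable with 40 practices and 18.1 with 45, at 80% power and two-sided 0.05.
- Implied standard error with 45 practices: 18.1/(1.960 + 0.842) = 6.46 points.
- Simple dilution: as-assigned effect = 19.4 × (1 − share leaving × share of the gain lost).
- All of the gain lost: 19.4 × 40/45 = 17.2. The difference is 2.2 points, and 2.2/6.46 = 0.33 standard errors.
- Half of it lost: 19.4 × 5/45 × 0.5 = 1.1 points, or 0.17 standard errors.
- None lost, or no true effect: 0.

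The documents do not say how leavers would behave, so the range from 0 to 2.2 points is an assumption. It would grow in proportion if more than 11% left.

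**6. Why a fixed multiplier is the wrong sensitivity parameter.** Multiplying imputed rates by 24.0/43.4 = 0.553 looks like loss of the whole gain. Under model (1), however, the intervention multiplies the rate by exp(β2 + β3(t − s)), which changes with time since start. The factor 0.553 undoes the planned gain only at the sixth quarter. With a growing effect it pushes earlier quarters below the no-intervention rate and leaves later ones above it.

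**The case against.** **The text is not contradictory.** The opening of 13.0 gives the intended schedule, and Analysis Considerations is a contingency. Over-enrolment to 45 is ordinary inflation. Two of the three fits use all practices, and imputation is meant to bring leavers in. This stands. A reader might infer that the passages conflict or that leavers' data will be discarded, and the documents support neither. They are silent on the rule.

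**Attrition may refer partly to other data.** Site-visit data and practice and staff surveys would stop at withdrawal even if extraction continued. That is possible, but the sentence names model (1), which points mainly to registry outcomes.

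**The plan does not promise to exclude bias.** It says understand, not rule out, and no analysis of observed data can rule out missing-not-at-random bias, a tipping-point analysis included. It also explores covariates and leaves room for other methods. All true. Covariates make missing at random more plausible but do not test it, and no other method is committed to. A tipping-point analysis at least states how large a departure would change the conclusion. The three-way comparison varies nothing of that kind.

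**The gap is mainly one of estimand.** When leavers are chosen at random and differ only after exit, the planned fits validly answer a different question. This stands too. The illustration does not model selective leaving, and there is no gap under no effect, so it gives no evidence of false-positive findings.

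**Availability is not assured.** The state program supplied rates for 53 practices before Aim II (3.0), which suggests that leavers' data could be obtained. But reporting to ALERT IIS is an eligibility condition under Aim I only (7.0). Nothing shows that the visit data needed for missed opportunities remain available after withdrawal.

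**Conclusion.** The concern holds in a limited form. The plan leaves open whether a withdrawn practice still contributes registry outcomes, and so leaves open whether the estimate describes assignment or continued participation. The three-way comparison cannot inform on missing-not-at-random bias, because all three fits, in standard form, assume missing at random or more.

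The likely consequence is small: between 0 and about 2.2 of 19.4 points, at most about a third of the implied standard error. This rests on 5 of 45 leaving, simple dilution, and leavers losing between none and all of the gain. A reader might infer that the trial's conclusion is at risk; nothing in the documents shows that. The case for acting is that the correction is cheap and is easiest to arrange before any practice leaves.

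**What to change.** In 13.0, Analysis Considerations:

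1. Define attrition, separating stopping the intervention from loss of registry data.
2. State that ALERT IIS outcomes are extracted through t = 13 for every randomised practice, whether or not it continues the intervention, where the registry and permissions allow.
3. State that the primary analysis includes all randomised practices by assigned start.
4. Limit imputation to practice-quarters whose registry data are truly absent.
5. For those, add a delta-adjusted (tipping-point) analysis. In the imputed quarters replace β2 + β3(t − s) by λ times that quantity, take λ from 1 (effect fully kept) to 0 (fully lost), and report where the conclusion changes. Do not use a fixed multiplier on the rates.
6. Keep the three-way comparison as a descriptive check, and do not present it as an assessment of missing-not-at-random bias.

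**Cost.** SAP wording and a line in the data request to the state program. Post-withdrawal extraction may need a permission that the documents do not show. The as-assigned estimate may be somewhat smaller: about 17.2 points if leavers gain nothing. On the implied standard error, power would then be Φ(17.24/6.46 − 1.96) = 76%, against the 80% stated for 19.4 points with 40 practices.

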## **14.0 RECRUITMENT METHODS**

Participating clinicians and practice staff members will be verbally asked if they agree to participate in the study after receiving a study information sheet at the start of baseline data collection (Aim I) [Note: The clinic team will receive a fact sheet – via in-person meetings with ORPRN staff and/or e-mail communication – that describes the study and all study activities prior to being asked to participate.]. Participation will be voluntary and will consist of agreeing to allow researchers to observe practice operations and interview practice clinicians and staff. For Aim II, clinicians and practice staff members will also be asked to complete study surveys at designated intervals. Patients selected to receive surveys will also receive information about the study, explaining how the data they provide on their surveys will be used. An information sheet about the study will be included with the survey mailings. Community partners will be identified by the participating practice members and project team members; these individuals will also receive a fact sheet about the study and an information sheet to help them decide whether or not to participate in the study.

